9.3. Setting

This study is a post-approval, company-sponsored, observational study in Japan.

9.3.1. Inclusion criteria

Patients must meet all of the following inclusion criteria to be eligible for inclusion in the study:

- 1) Diagnosed with locally advanced or metastatic UC before receiving Avelumab 1L maintenance therapy
- 2) Started 1L maintenance therapy with avelumab for locally advanced or metastatic UC from 24 Feb 2021 (launch date) to 30 Nov 2021
- 3) Evidence of a personally signed and dated informed consent document indicating that the patient (or a legally acceptable representative) has been informed of all pertinent aspects of the study
 - (1) Written consent is not required for patients who were transferred to a hospital, and registration with verbal consent is acceptable
 - (2) Opt-out enrollment is allowed for patients who have already died
- 4) Deceased patients are also required to meet the inclusion criteria 1)-2)

9.3.2. Exclusion criteria

There are no exclusion criteria for this study.

[figure not shown]

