7. RATIONALE AND BACKGROUND

[figure not shown]
Bladder cancer accounts for approximately 90% of Urothelial carcinoma (UC). Approximately 550,000 cases of bladder cancer are newly diagnosed worldwide each year¹. Each year, 200,000 cases of death are caused by bladder cancer. Bladder cancer incidence and death rates have not changed by 25 annuals². According to the cancer statistical forecast in 2021 conducted by the National Cancer Center Japan, the estimated number of bladder cancers and deaths in 2021 in Japan were 24,300 and 9,700, respectively³. Patients with metastatic UC have a dismal prognosis with a 5-year survival rate of only 5%. Platinum-based polychemotherapy regimen is currently the first-line (1L) standard of care (SOC) for patients with advanced/metastatic disease, but despite high initial response rates, durable and complete responses following 1L chemotherapy (Cht) are uncommon, and most patients will ultimately experience disease progression within 9 months after initiation of treatment⁴.

CCI

CCI

Avelumab (MSB0010718C, BAVENCIO®) is a human immunoglobulin G1 monoclonal antibody directed against the programmed death ligand 1 (PD-L1). In Japan, Cht is the 1L SOC recommended in guidelines for locally advanced or metastatic UC; CCI

CCI

Avelumab in combination with best supportive care (BSC) as a maintenance treatment had been evaluated versus BSC alone in a Phase 3 randomized trial (JAVELIN Bladder 100) in patients with locally advanced or metastatic UC who had not progressed with 1L platinum-based Cht. The JAVELIN Bladder 100 study has demonstrated a significant 7.1-months improvement in median OS with Avelumab+BSC as 1L maintenance versus BSC alone (median OS, 21.4 months vs 14.3 months), with a 31% reduction of the death risk in the overall population (hazard ratio = 0.69 (95% confidence interval [CI], 0.56, 0.86), p=0.001)⁸. The results of Japanese subgroup analysis in the JAVELIN Bladder 100 were generally consistent with those in the overall population⁹. CCI

The present study, B9991048, aims to evaluate the demographic and baseline disease characteristics and current treatment outcomes in patients with locally advanced or metastatic UC treated with avelumab those who had been prescribed Avelumab in a period of 9 months after launch, and had a follow-up duration of 7 months. In CCI

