9.2. Endpoint

9.2.1. Primary endpoint

Patient characteristics at baseline (at the initiation of 1L Cht and the initiation of avelumab maintenance therapy)

The following baseline (at the initiation of 1L Cht and the initiation of avelumab maintenance therapy) patient background will be collected. The latest data before the start of 1L Cht and before the start of avelumab administration will be collected, respectively.

- 1) Age*
- 2) Sex*
- 3) Medical history/comorbidity (interstitial lung disease/chronic obstructive pulmonary disease/autoimmune disease/cerebrovascular disease/cardiovascular disease/diabetes/others) *
If these diseases are cured by the start of avelumab administration, they are treated as a medical history, and if they continue after avelumab administration, they are treated as comorbidity.
- 4) Confirmed date of urothelial carcinoma
- 5) Eastern Cooperative Oncology Group (ECOG)
- 6) Tumor-node-metastasis (TNM) classification
- 7) Cht regimens received in 1L (Cisplatin [Cis]/ Gemcitabine [Gem], Carboplatin [Carbo]/Gem, Methotrexate, Vinblastine, Adriamycin, and Cisplatin [MVAC] regimens, dose dense-MVAC, others)
- 8) Start date and end date of administration, Number of Cht cycles received in 1L
- 9) Duration between the end date of 1L Cht and the start date of avelumab
- 10) Best overall response to 1L Cht (complete response [CR], partial response [PR], stable disease [SD], PD)
- 11) Site (bladder, urethra, renal pelvis or ureter) and histology (Urothelial carcinoma/ adenocarcinoma/ squamous cell carcinoma/ small cell carcinoma/others [details]) of the primary tumor at the time of initial diagnosis.
- 12) Histological atypia
- 13) Histological depth of tumor invasion
- 14) Definitive treatment of primary lesion (Yes [Surgery/ Others]/ No), date of treatment.

15) Site of distant metastasis (Yes [visceral/ non visceral]/ No)

Visceral: Having to do with the viscera, which are the soft internal organs of the body, including the lungs, the heart, and the organs of the digestive, excretory, reproductive, and circulatory systems (Classified as "visceral" if it has visceral metastasis, and classified as "non-visceral" if it has only locally advanced / recurrent lesions and non-visceral lesions without visceral metastasis)

16) Local recurrence (Yes/No), if yes, recurrence confirmed date

17) Bajorin risk classification (0/1/2)

<Bajorin risk classification¹⁰>

Risk factor	Classification	
• Visceral metastases	No risk factor	0

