5.1 Analysis set/populations

Among patients who were enrolled in the study and received maintenance avelumab treatment between 24 February 2021 and 30 November 2021, patients meeting all the inclusion criteria will be analyzed.

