	Primary tumor (T factor)	Reginal lymph nodes (N factor)	Distant metastasis (M factor)	Clinical stage
	Ta	N0	M0	0a
	Tis	N0	M0	0is
	T1	N0	M0	I
	T2	N1	M0	II
	T1, T2	N1	M0	III
	T3	N0, N1	M0	III
	T4	N0, N1	M0	IV
Clinical stage classification: Renal pelvis, Ureter	Any T	N2	M0	IV
	Any T	Any N	M1	IV
	Clinical stage is categorized using primary tumor (T factor), reginal lymph nodes (N factor), distant metastasis (M factor) as follows.			
	Primary tumor (T factor)	Reginal lymph nodes (N factor)	Distant metastasis (M factor)	Clinical stage
	Ta	N0	M0	0a
	Tis	N0	M0	0is
	T1	N0	M0	I
	T2	N0	M0	II
	T3	N0	M0	III
Treatment-free interval: Time from the end date of first-line chemotherapy to the start date of avelumab administration (3 divisions)	T4	N0	M0	IV
	Any T	N1、N2	M0	IV
	Any T	Any N	M1	IV
Response (avelumab maintenance)	Time from the end date of first-line chemotherapy to the start date of avelumab administration is divided into the following categories. <4 weeks/4 to 10 weeks/>10 weeks			
	Determination of the best overall response to avelumab maintenance is categorized as following: "Objective response" when "CR" or "PR." "Non-objective response" when "SD" or "PD"			
	Determination of the best overall response to first-line chemotherapy is categorized as following:			

	
"Objective response" when "CR" or "PR."
 
"Non-objective response" when "SD" or "PD"

Best overall response to first-line chemotherapy (2)	Determination of the best overall response to first-line chemotherapy is categorized as following: CR + PR/SD
Presence or absence of prednisolone	"Presence" will be selected when "prednisolone" is selected for the corticosteroid administration drug name, and "absence" will be selected when "No" is selected for the drug name.
Presence or absence of methylprednisolone	"Presence" will be selected when "methylprednisolone" is selected for the corticosteroid administration drug name, and "absence" will be selected when "No" is selected for the drug name.
Presence or absence of betamethasone	"Presence" will be selected when "betamethasone" is selected for the corticosteroid administration drug name, and "absence" will be selected when "No" is selected for the drug name.
Presence or absence of dexamethasone	"Presence" will be selected when "dexamethasone" is selected for the corticosteroid administration drug name, and "absence" will be selected when "No" is selected for the drug name.

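### The requirement for 1L maintenance is not defined as non-progression, so patients with PD on 1L chemotherapy are not clearly screened out of the effectiveness estimates

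*Protocol*

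**What the plan says.** **Eligibility.** Protocol 9.3.1 has two clinical criteria. Criterion 1 is "Diagnosed with locally advanced or metastatic UC before receiving Avelumab 1L maintenance therapy". Criterion 2 is "Started 1L maintenance therapy with avelumab for locally advanced or metastatic UC from 24 Feb 2021 (launch date) to 30 Nov 2021". The others concern consent and deceased patients. Protocol 9.3.2 states "There are no exclusion criteria for this study". No criterion refers to response to 1L chemotherapy or to disease status at the start of avelumab, and the readable text does not define maintenance.

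**Reference population.** Only the background (Protocol 7) mentions non-progression. It describes the randomised trial of avelumab as having enrolled patients "who had not progressed with 1L platinum-based Cht".

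**Planned response levels.** Protocol 9.2.1, item 10, collects "Best overall response to 1L Cht (complete response [CR], partial response [PR], stable disease [SD], PD" as a baseline variable. SAP 7.1 tabulates the same four levels.

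**Derived variables.** SAP 5.5 derives two groupings of best response to 1L chemotherapy. One puts CR and PR in an objective-response group and SD and PD in a non-objective group. The other, numbered (2), reads "Determination of the best overall response to first-line chemotherapy is categorized as following: CR + PR/SD".

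**Analysis set.** SAP 5.1 defines one set: of the enrolled patients who received maintenance avelumab in the window, "patients meeting all the inclusion criteria will be analyzed". SAP 8.1.1 to 8.1.4 use it for TTF, rwPFS, ORR and rwPFS-c.

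**The concern.** Secondary objective 1 (Protocol 8.2) is the effectiveness of 1L maintenance. A patient whose disease progressed on chemotherapy and who then started avelumab is being treated after failure, which is a different clinical situation with a different expected course. If such patients are in the set, the TTF, rwPFS and ORR results describe a mix of the two situations, and nothing in the readable outputs separates them.

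rwPFS-c has a further difficulty because its clock starts at 1L chemotherapy. SAP 5.5 counts the first progression or death, without qualification. For a patient who progressed on chemotherapy, that event precedes the first avelumab dose. Protocol 9.2.2 and 9.2.3.4 add that the event is during avelumab treatment. The two documents can therefore give different event dates for these patients.

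**Working it through.** **1. Can a PD patient be in the set?** Setting the texts side by side:

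| Place | Effect on a patient with PD on 1L chemotherapy |
|---|---|
| Protocol 9.3.1, criterion 1 | No effect; concerns diagnosis only |
| Protocol 9.3.1, criterion 2 | Excludes the patient only if the site reads maintenance as non-progression |
| Protocol 9.3.2 | No exclusion |
| Protocol 9.2.1 item 10; SAP 7.1 | PD is an available level |
| SAP 5.5, two-group response variable | PD is grouped with SD |
| SAP 5.5, variable (2) | PD has no level |
| SAP 5.1; 8.1.1 to 8.1.4 | No further filter |

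Criterion 2 is the only possible barrier, and it depends on an undefined word. The two SAP 5.5 variables do not agree on whether PD can occur.

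**2. How much could it matter?** The plan has no figure to reproduce: the planned number of patients is redacted, and no response or progression rates are given. The following is for scale only.

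Assume exponential rwPFS with median *a* months in non-progressed patients and 2 months in patients who progressed on chemotherapy, the latter making up a share *p*. Then

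S(t) = (1 − p) · 0.5^(t/a) + p · 0.5^(t/2), and the pooled median solves S(t) = 0.5.

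| a (months) | p | Pooled median (months) | Change from a |
|---|---|---|---|
| 6 | 5% | 5.68 | −5.4% |
| 6 | 10% | 5.36 | −10.6% |
| 8 | 5% | 7.49 | −6.3% |
| 8 | 10% | 6.99 | −12.6% |

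Check of the first row: 0.95 × 0.5^(5.68/6) + 0.05 × 0.5^(5.68/2) = 0.493 + 0.007 = 0.500.

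Six-month rwPFS with a = 6 is 0.95 × 0.5 + 0.05 × 0.125 = 0.481 at p = 5%, and 0.90 × 0.5 + 0.10 × 0.125 = 0.463 at p = 10%, against 0.500 at p = 0.

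**3. Sensitivity to the contrast.** The medians above imply hazard ratios of 6/2 = 3 and 8/2 = 4. Solving the same equation with the hazard ratio *h* as the input gives these reductions in the pooled median:

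| p | h = 1.5 | h = 2 | h = 3 |
|---|---|---|---|
| 2% | 0.8% | 1.4% | 2.2% |
| 5% | 2.1% | 3.6% | 5.4% |
| 10% | 4.1% | 7.0% | 10.6% |
| 15% | 6.1% | 10.4% | 15.7% |

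The effect is small if PD patients are few and noticeable at about 10% or more.

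**The case against.** The strongest reply is that criterion 2 already does the work: a patient treated after progression is not on maintenance and so fails it. CR/PR/SD/PD is the standard response list, so printing PD need not mean that PD patients are expected, and the variable with no PD level suggests that none were. This stands in part. A reader might infer that the plan accepts or expects such patients; the documents show only that it does not clearly screen them out. Sites still have no rule to apply, and the SAP gives PD a place in two of its three 1L response classifications.

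Other tempting readings also go too far.
- The regimen category for others does not show non-platinum therapy. M-CAVI, which contains carboplatin, is in the abbreviation list but is not a named regimen and would fall there.
- Criterion 1 dates the diagnosis relative to avelumab rather than chemotherapy, which might suggest that chemotherapy for earlier-stage disease could count as 1L. Criterion 2 ties 1L maintenance to locally advanced or metastatic disease, and the background uses 1L in that sense.
- It cannot be said that no analysis by 1L response exists. SAP text between 8.2.5 and 11 is redacted, and several derived groupings, including variable (2), appear in no readable analysis.

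It is also fair that the study is single-arm with a descriptive primary objective, which broad eligibility suits; that SAP 7.1 will show the number of PD patients; and that no readable section plans a comparison with the randomised trial. Sampling error may exceed the shift: for an assumed n of 50 to 300, the 95% half-width around a 50% rate, ignoring censoring, is 1.96 × √(0.25/n), or about 14 to 6 percentage points, against a shift of 2 to 4 points in six-month rwPFS. But the shift is a systematic change in what is estimated, and a count in a baseline table does not remove it from the four outcomes.

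**Conclusion.** The point holds as a gap in definition. Maintenance is required but not tied to non-progression, PD is a tabulated 1L response, the SAP is inconsistent about where PD belongs, and the visible main estimates of all four effectiveness outcomes use one unfiltered set. It bears on secondary objective 1, not on the primary descriptive objective.

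The size is unknown. The figure of about 5% to 13% off the pooled median rwPFS rests on assumed exponential times, medians of 6 to 8 months against 2 months, and a PD share of 5% to 10%. A hazard ratio of 1.5 brings it down to about 2% to 4% for the same shares. If no PD patients were enrolled, the effect is nil. The change is worth making because it is cheap and lets objective 1 be answered for maintenance as such; the documents do not show that the estimates are in fact distorted.

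**What to change.** Leave eligibility and the full analysis set unchanged. In the SAP, before data lock:

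1. Add to 5.1 a supplementary effectiveness set: patients with best overall response CR, PR or SD to 1L chemotherapy and, where the chart records it, no documented progression between the start of 1L chemotherapy and the index date. The second condition is needed because a patient who first responded may have progressed before avelumab.
2. Report TTF, rwPFS, ORR and rwPFS-c in this set beside the full set, with the number of patients removed and the reasons.
3. Add a PD level to *Best overall response to first-line chemotherapy (2)*, or state how PD is handled there.
4. Reconcile the SAP 5.5 definition of rwPFS-c with the protocol's restriction to events during avelumab treatment.

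Rewriting criterion 1 is not recommended. It would be a protocol amendment, it would conflict with keeping all patients, and no listed data item dates the diagnosis of locally advanced or metastatic disease.

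The cost is some SAP wording and one repeat of four existing outputs. Best response to 1L chemotherapy is already collected; progression before the index date can be applied only where the chart records it. The downside is slightly wider intervals in the smaller set.

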9.4. Variables

Collect the information shown in Sections 9.2.1 and 9.2.2 in this study. Human genome and gene information will not be collected.

9.5. Data sources

As this is a retrospective study, all data will be collected from medical records at the participating study site in Japan.

CCI

9.7. Data management

Investigators will fill out electronic case report forms (eCRFs) based on the medical charts by electronic data capture (EDC). After the completion, eCRFs are transferred to a single electronic database. Only the de-identified and pseudonymized data are included. When receiving a query from the data manager on the completed eCRF (ie, data clarification form [DCF]), investigators will reconfirm the information on source documents, fill out the DCF as required, and submit the DCF.

9.7.1. Case report forms (eCRFs)/Data collection tools (DCTs)/Electronic data record

As used in this protocol, the term CRF should be understood to refer to an electronic data record or both, depending on the data collection method used in this study. An eCRF is required and should be completed for each included patient. The completed original eCRFs are the sole property of Pfizer and should not be made available in any form to third parties, except for authorized representatives of Pfizer or appropriate regulatory authorities, without written permission from Pfizer.

The investigator shall ensure that the eCRFs are securely stored at the study site in encrypted electronic form and will be password protected to prevent access by unauthorized third parties. The investigator has ultimate responsibility for the collection and reporting of all clinical, safety, and laboratory data entered on the eCRFs and any other data collection forms (source documents) and ensuring that they are accurate, authentic/original, attributable, complete, consistent, legible, timely (contemporaneous), enduring, and available when required.

The eCRFs must be signed by the investigator or by an authorized staff member to attest that the data contained on the eCRFs are true. Any corrections to entries made in the eCRFs or source documents must be dated, initialed, and explained (if necessary) and should not obscure the original entry. The source documents are the hospital or the physician's chart. In these cases,

9.7.2. Record retention

To enable evaluations and/or inspections/audits from regulatory authorities or Pfizer, the investigator agrees to keep records, including the identity of all participating patients (sufficient information to link records, eg, eCRFs and hospital records), all original signed informed consent documents, copies of all eCRFs, safety reporting forms, source documents, detailed records of treatment disposition, and adequate documentation of relevant correspondence (eg, letters, meeting minutes, and telephone call reports). The records should be retained by the investigator according to local regulations or as specified in the clinical study agreement (CSA), whichever is longer. The investigator must ensure that the records continue to be stored securely for so long as they are retained.

If the investigator becomes unable for any reason to continue to retain study records for the required period (eg, retirement, relocation), Pfizer should be prospectively notified. The study records must be transferred to a designee acceptable to Pfizer, such as another investigator, another institution, or to an independent third party arranged by Pfizer.

Study records must be kept for a minimum of 15 years after completion or discontinuation of the study, unless the retention period is specified in the contract between each research institution and Pfizer or required by the regulations of the implementing country. Record must be retained for longer than 15 years if required by applicable local regulations.

The investigator must obtain Pfizer's written permission before disposing of any records, even if retention requirements have been met.

9.7.3. Record disposal

Study records must be disposed of appropriately according to each site regulation.

9.8. Data analysis

Detailed methodology for summary and statistical analyses of data collected in this study will be documented in a Statistical Analysis Plan (SAP), which will be dated, filed, and maintained by the sponsor. The SAP may modify the plans outlined in the protocol; any major modifications of primary endpoint definitions or their analyses would be reflected in a protocol amendment. The SAP must be finalized before data lock. The final analysis will be performed after data lock and may modify the plans outlined in the protocol.

9.8.1. Analysis Population

The analysis population is defined in the SAP.

9.8.2. Analysis Methods

Continuous variables will be summarized using descriptive statistics ie, number of nonmissing values and number of missing values [ie, n (missing)], mean, median, standard deviation (SD), minimum, maximum and first and third quartile. Qualitative variables will be summarized by frequency counts and percentages. These endpoints will also be displayed graphically, if necessary.

9.8.3. Analysis of Primary Endpoints

See 18. These endpoints will be descriptively summarized. These endpoints will also be displayed graphically, if necessary.

9.8.4. Analysis of Secondary Endpoints

Efficacy Endpoints

See 19. For the time-to-event endpoints, eg, TTF and rwPFS, the Kaplan-Meier estimates (product-limit estimates) will be presented together with a summary of associated statistics including the median time with 2-sided 95% CIs. In particular, the survival rate at several timepoints will be estimated with corresponding 2-sided 95% CIs.

Other Secondary Endpoints

See 19. These endpoints will be descriptively summarized. These endpoints will also be displayed graphically, if necessary.

9.9. Quality control

The sponsor will train investigators and study site staff with an onsite training visit or web training on the protocol, eCRFs, and any applicable study processes. Any new information relevant to the performance of this study will be forwarded to the investigator and study site staff during the study. Remote data monitoring will be conducted during the life of the study to ensure timely reporting of data, data integrity, and consistency. eCRFs for all included patients will be made available to the remote data monitor for review. The study sites will be queried and managed to request resolution to any issues that may arise during the course of the study.

